Neuroimaging the Expectancy versus Pharmacotherapy Effect of Adderall on Cognitive Performance

Study Protocol

NCT03603028

May 15, 2019

[name], Principal Investigator University of Alabama at Birmingham Birmingham, AL 35294

Neuroimaging the Expectancy versus Pharmacotherapy Effect of Adderall on Cognitive Performance

Primary Investigator:

[name]
The University of Alabama at Birmingham
[name]
[contact]

[contact]

Study Summary

Title Neuroimaging the Expectancy versus Pharmacotherapy Effect of						
	Adderall on Cognitive Performance					
Methodology	Double blind, within subjects, balanced placebo, randomized controlled clinical trial.					
Study Duration	Estimated duration for the main protocol (e.g. from start of study to finishing the study) is approximately 1 year.					
Study Center(s)	The University of Alabama at Birmingham – Highlands Hospital and the Sparks Center, Birmingham, AL					
Objectives	To further explore the relationship between stimulant medication and its effect on cognitive function, specifically whether participants' expectations regarding the benefits of stimulant medication affects their performance on neurocognitive tasks.					
Number of Subjects	10 (4 to complete the study, and 6 alternate participants).					
Diagnosis and Main Inclusion Criteria	Inclusion Criteria - Age (18-24) - College student with at least average IQ - Willingness to standardize caffeine intake to 100mg on day of study Exclusion Criteria - Diagnosis of ADHD - Unwillingness to comply with caffeine specifications - Regular use of Adderall - Pregnant/breastfeeding - History of substance use disorders - Illicit stimulant use within the last year - Contraindications to stimulants (i.e., tics, Tourette's, cardiac disease, hypertension) - Uncontrolled medical illness - Active contagious infection					
Study Product, Dose, Route,	Study Product: Dextroamphetamine-amphetamine & Placebo, Dose: 10mg					
Regimen	Route: Oral Regimen: One dose in the AM at Imaging visits					

1. Introduction

1.1 Background

The conceptualization of prescription stimulant medications as cognitive enhancers is weakly supported by science. Nonmedical use of prescription stimulants for the purpose of academic enhancement is rampant in institutes of higher learning with potent negative public health implications. A recent series of recent military studies of healthy subjects comparing prescription stimulants to the ubiquitous caffeine and less abuse-prone modafinil demonstrated equivalent benefits between stimulants in sustaining alertness and attention during fatigue states. No improvement in higher order thinking skills (aka. cognitive enhancement) was noted for any stimulant. Nevertheless, 44% of healthy college students see prescription stimulants as superior to caffeine for cognitive enhancement (Franke, 2012). Evidence for prescription stimulants as cognitive enhances is lacking: two studies found dextroamphetamine improved a single measure of verbal memory, however, a number of studies have demonstrated that a 60-90 minute nap resulted in consolidation of memory on multiple measures.

Young adults have misconceptions about prescription stimulants. The majority of undergraduate students overestimated the prevalence of non-medical use of prescription stimulants (70.2%) among peers on their campus. Additionally, opinions about the use of illegally acquired substances were partly based on evidence based medical facts, but were also strongly influenced by their individual preferences of substances used for cognitive enhancement (Frank 2012). Among college students, actual self-reported non-medical use of prescription stimulants rates range from 1.5% to 31% between survey studies (Mcabe, 2008) with the majority reporting that the primary reason for use was to improve academic performance. (Bogle, 2009) In one survey, 11.3% of students in health care professional schools admitted to nonmedical prescription stimulants use for the purpose of: enhancing alertness/energy (65.9%), to improve academic performance (56.7%), to experiment (18.2%), and to use recreationally/get high (4.5%) (Bossier, 2013). The lifetime prevalence of prescription stimulant use in a sample of 144 medical students was 20%, with 15% using during medical school. 83% reported using them specifically for cognitive performance enhancement such as studying more effectively and staying awake longer. (Webb, 2013) (Arria). Substance abuse in late adolescence is more dependent on peer exposure to drug-abusing peers than intrinsic factors. (NIH, National Institute on Drug Abuse Website www.drugabuse.org)(Gerstein and Green 1993; Dishion et al. 1999). Accurate differentiated empiric data about the true benefit/risk ratio of prescription stimulants to caffeine and in healthy subjects vs. ADHD subjects could reduce nonmedical use resulting from peer-peer misinformation (Hawkins et al. 2002) (Frank, 2012).

The cognitive effect of prescription stimulants on normal healthy adults has not been

characterized definitively. No studies have shown that cognitive gains from prescription stimulants exceed the benefits from caffeine, a less risky and legal product. Since caffeine is well known to enhance attention and vigilance during fatigue states, subjects desirous of cognitive enhancement are presumably seeking to enhance high order thinking such as learning and memory. In a double blind placebo-controlled crossover study, 19 healthy young male volunteers were tested after a single dose of placebo or methylphenidate. Declarative memory consolidation was significantly improved relative to placebo for the 20 and 40 mg methylphenidate states as measured by a word-learning test, but not on spatial working memory or a planning task. (Linnsen, 2012). Another double-blind, cross-over placebo controlled study assessed healthy controls on 13 measures of cognitive abilities and found no cognitive enhancement from stimulant medication. However, subjects in this study believed their performance was enhanced by the stimulant medication (Illieva, Boland, & Farah, 2013).

A previous study conducted by the principal investigator and one of the co-investigators of this proposed study involved the administration of a neurocognitive battery to healthy controls after receiving either stimulant medication or placebo. Participants were either accurately or inaccurately informed whether they received medication or placebo. Out of 31 subtests, participants only showed improvement on two of the subtests during active medication. Expecting stimulant medication was associated with improved cognitive performance and expecting placebo was associated with worse cognitive performance, regardless of the type of medication given. The results of this study demonstrated that individuals' expectancies influenced cognitive performance while the use of stimulant medication did not ([name] et al. 2017).

2. Study Objectives

To further explore the relationship between stimulant medications and its effect on cognitive function, specifically whether participants' expectations regarding the benefits of stimulant medication affects their performance on neurocognitive tasks. We were interested in examining feasibility and acceptability of administering Adderall and neuroimaging while completing tasks in the scanner.

3. Study Design

3.1 General Design

This is a within subjects 2 x 2 design, in which all participants will experience all four conditions during four sequential weeks. Medication administered (Adderall vs. placebo) will be crossed with instructional set (truth vs. deception) and participants' performance on neurocognitive tasks will be compared across these groups. For example, participants will be told either accurately or inaccurately that they are receiving Adderall or placebo. This creates four conditions that will be delivered over four weeks (see table below). The presentation of these conditions will be counterbalanced across the four weeks for each of the participants, such that they will not

receive the same ordering of conditions.

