3.2 Primary Study Endpoints

Feasibility and acceptability of imaging college-age participants administered Adderall or placebo.

4. Subject Selection and Withdrawal

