4.4 Early Withdrawal of Subjects

4.4.1 When and How to Withdraw Subjects

Students will be informed they may withdraw from the study at any time, for any reason, before it is completed. They will be informed that their participation will not affect their class standing or grades at UAB. They will not be offered or receive any special consideration if they take part in the research. Employees will be informed that taking part in the research is not part of their UAB duties and refusing to be a part of the study will not affect their job or relationship with UAB. They will not be offered or receive any special job-related consideration if they take part in this research.

5. Study Drug

Dextroamphetamine-amphetamine & Placebo

6. Study Procedures

Study Appointment (2-3 hours): Pulse and blood pressure will be measured before medication is administered. If pulse and blood pressure are within acceptable limits, medication will be administered. A potential side effect checklist (attached) will be reviewed after the period of time in which medication effects would become active. Any reported side effects will be addressed prior to continuation of the session. The MRI safety questionnaire will be reviewed and signed at each scanning visit. This questionnaire will be filed at the CINL. Any abnormal findings will be discussed with physician investigator who will determine if the subject is fit to participate in the study.

The participant will be given either a placebo or Adderall depending on randomization. Each participant (N = 4) will either be told that he/she is receiving Adderall or placebo, as indicated on pre-labeled medication bottles to preserve the double-blind nature of the study. The participant will either receive medication or placebo as they are informed, not receive medication when they believe they are receiving medication, or will receive medication when they believe they are not receiving medication. This will allow for measurement of expectancy, which is a core measure for this study. This study design makes the comparison of cognitive performance based on actual versus perceived benefit possible. Presented below is an example table of study conditions.

Conditions will be counterbalanced across participants to control for order effects.

	Week 1	Week 2	Week 3	Week 4	
Expecting	Adderall	Adderall	Placebo	Placebo	
Medication	Adderall	Placebo	Placebo	Adderall	

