(Expecting refers to whether participants are told that they are taking Adderall or a placebo pill. Medication refers to the pill that participants are actually receiving.)

Before the medication is administered and after the MRI scan, participants will complete the POMS (Profile of Mood States) to measure mood and euphoria (attached). Participants will also self-report on their perceived mental acuity pre-dose and after each cognitive task (described below) performed in the scanner on a scale of 0-100with 100 indicating "more sharp than normal."

Cognitive testing will be timed to begin 45 minutes after medication or placebo is given.

Participants will then start the magnetic resonance spectroscopy scanning portion of the session, which will take one hour. The MRI scan will not include the use of a contrast agent. A 3 Tesla Siemens Prisma scanner and 20-channel head coil will be used. Scan sequences are listed below:

- Auto-align scout (1 min): to determine brain orientation and slice prescription. Will use 260mm field of view (FOV), 160 x 160 matrix, 3.15ms repetition time (TR), 1.37ms echo time (TE), 1.6mm slice thickness, no gap. The scout data are not used in post-scan analyses, so processing and analysis steps are not described.
- T1-weighted magnetization prepared rapid gradient echo (MPRAGE) high-resolution scan (10 min): for anatomical localization and to achieve standard space for group analyses.
 Will use 230mm FOV, 256 x 256matrix, 2000ms TR, 2.51ms TE, 0.9mm slice thickness, and no gap, yielding 0.9x0.9x0.9mm voxels.
- Functional MRI (60 min): Axial T2*-weighted images will be acquired using an echoplanar sequence 220x220 FOV, 64x64 matrix, 2000ms TR, 28ms TE, 3mm slices, yielding 3x3x3 mm voxels. Heart rate and respirations will be measured continuously in the scanner.
 - Participants will complete a "resting state" scan in which they are instructed to close their eyes and rest.
 - While undergoing fMRI scans, participants will complete three different cognitive
 tasks measuring aspects of sustained attention, new learning, and working memory.
 Participants will receive a short explanation of each task, as well as sample items,
 prior to entering the scanner, and will be able to have their questions answered.
 Specific task instructions will also be presented on screen inside the scanner prior to
 each task.
 - The first task will utilize a paced serial addition paradigm. Participants will be

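### Does labelling the second factor truth versus deception leave the 2 x 2 unable to measure expectancy?

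*Protocol*

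**What the plan says.** Section 3.1 (General Design) of the Protocol describes a within-subject 2 x 2: "Medication administered (Adderall vs. placebo) will be crossed with instructional set (truth vs. deception". It adds that "participants' performance on neurocognitive tasks will be compared across these groups" and that "all participants will experience all four conditions during four sequential weeks". It names no model, contrast or main-effect test, and it refers the reader to a table of conditions.

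That table is in Section 6 (Study Procedures). Its two rows are Expecting and Medication, and the note beneath it reads: "Expecting refers to whether participants are told that they are taking Adderall or a placebo pill". Of the arrangement of cells, Section 6 says: "This will allow for measurement of expectancy, which is a core measure for this study".

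Section 2 (Study Objectives) puts the question in the same terms: "specifically whether participants' expectations regarding the benefits of stimulant medication affects their performance on neurocognitive tasks". Section 1.1 (Background) reports the team's previous study: "Expecting stimulant medication was associated with improved cognitive performance and expecting placebo was associated with worse cognitive performance, regardless of the type of medication given".

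In Section 3.2 the primary endpoint is "Feasibility and acceptability of imaging college-age participants administered Adderall or placebo". The Study Summary plans for 4 completers, with 6 alternates.

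**The concern.** Sections 3.1 and 6 name different second factors for one 2 x 2, and the two are not interchangeable as main effects. Truth pools the told-Adderall/got-Adderall cell with the told-placebo/got-placebo cell. Deception pools the other two. Each level is therefore half told-Adderall and half told-placebo, and an expectancy effect cancels between them.

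The pattern reported from the previous study, an effect of expectation whichever pill was given, is the very case in which both declared main effects are zero. An analyst who tested only the two factors named in Section 3.1, and took the second as expectancy, would report that neither drug nor instruction mattered although expectancy was at work. The stake would be a false null on what the Protocol calls a core measure.

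**Working it through.** The Protocol gives no effect size, SD, alpha or power for this comparison, so there is no figure of its own to reproduce. The check is contrast algebra on the four cells of the Section 6 table.

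**Notation.** The first letter is what the participant is told and the second is what is received (A = Adderall, P = placebo). In table order the cell means are AA, AP, PP, PA.

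**Contrasts.**

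- Medication = (AA + PA)/2 − (AP + PP)/2
- Truth/deception = (AA + PP)/2 − (AP + PA)/2
- Told (expectancy) = (AA + AP)/2 − (PP + PA)/2
- Medication x instruction, as half the difference of differences. The truth effect on Adderall is AA − PA, and on placebo it is PP − AP. Half their difference is [(AA − PA) − (PP − AP)]/2 = (AA + AP − PP − PA)/2.

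The last line is identical to the told contrast. In signs, told = (+,+,−,−), medication = (+,−,−,+) and truth = (+,−,+,−). The three are mutually orthogonal, and the product of any two is the third.

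**Expectancy only, size d.** AA = AP = d and PP = PA = 0.

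- Medication: (d + 0)/2 − (d + 0)/2 = 0
- Truth/deception: (d + 0)/2 − (d + 0)/2 = 0
- Medication x instruction: [(d − 0) − (0 − d)]/2 = d
- Told: (d + d)/2 − 0 = d

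**Four scenarios, unit effects.**

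| Scenario | Medication main | Truth/deception main | Medication x instruction | Told main |
|---|---|---|---|---|
| Expectancy only | 0 | 0 | 1 | 1 |
| Drug only | 1 | 0 | 0 | 0 |
| Drug and expectancy, additive | 1 | 0 | 1 | 1 |
| Drug-by-expectancy only | 0 | 1 | 0 | 0 |

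The last two columns agree in every row. The truth/deception main effect is the drug-by-expectancy interaction.

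**Same model, same precision.** The design matrix with medication, truth and their product has rank 4. So has the one with medication, told and their product, and the two placed side by side still have rank 4. They are one saturated model under two sets of labels.

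For precision, assume 4 participants, an expectancy effect of 1 and a within-subject SD of 1 (the last two are assumptions; the Protocol gives neither). Participant effects cancel, and each contrast is a mean of 8 sessions minus a mean of 8 sessions, so its standard error is √(1/8 + 1/8) = 0.5. In 20,000 simulated trials the declared interaction and the told main effect both averaged 1.00 with SD 0.499. They differed by at most about 1e-15, which is rounding error.

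**The case for a change.** The strongest case for a change is that this is more than an unstated contrast. The design section names a factor that is not the one of interest and does not match the document's own table and objective. A statistical analysis plan that copied Section 3.1 would inherit the label, and a reader who looks first at main effects could be misled in exactly the scenario the investigators expect. The cure would be one sentence.

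The mismatch in labels stands, and so does the zero main effect. What does not stand is the step from there to a comparison that fails. The misreading needs three moves: fit main effects only, drop the interaction, and read truth/deception as expectancy. The Protocol asks for none of them. It describes crossed factors and a comparison across all four conditions, which contains the told contrast.

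Nor do the two descriptions conflict about what is done. The pill received, together with whether the information is accurate, fixes what the participant was told. Section 3.1 describes how the cells are produced, and Section 6 describes the same cells by what is believed. Section 1.1 itself describes the previous study's manipulation in terms of accurate and inaccurate information, yet reports its result by expectation. The wording did not lead to a misreading there. Named contrasts would in any case normally sit in a statistical analysis plan, which is not at hand.

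**Conclusion.** The concern is right on the algebra: truth versus deception is not expectancy, and its main effect is exactly 0 when expectancy acts alone or adds to a drug effect. It fails on the consequence. The declared factors recover all of the expectancy effect through their interaction, with the same estimate and standard error as under the other labels, so nothing is lost. What remains is a difference in terminology that the Section 6 table and its note resolve. Matching the label in Section 3.1 to the table would be harmless tidying, but no cell, datum or estimate depends on it.

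This rests on two assumptions. All four conditions are analysed with the interaction retained, as a comparison across all four cells implies. And whoever analyses the data uses the table's definition of expectancy. The practical weight is small in any event: the primary endpoint is feasibility and acceptability, 4 completers are planned, and Section 10 does not expect the results to be published.

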9.3 Subject Stipends or Payments

Participants will receive \$50 for the screening visit and \$100 for the 4 scanning visits for a maximum of \$450 per participant. If the participant does not complete the study, payments will be prorated to pay them for the visits they did complete. Payments will be processed after participants complete the study by mail.

10. Publication Plan

This is an acceptability/feasibility study. Given the small sample size, we do not anticipate publishing results.

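### Does the protocol's counterbalancing rule fail to control order effects, and must it say which order an alternate takes?

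*Protocol*

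**What the plan says.** Section 3.1 describes a within-subject 2 x 2 design in which every participant meets all four conditions over four weeks. On order it states: "The presentation of these conditions will be counterbalanced across the four weeks for each of the participants, such that they will not" (the sentence ends by ruling out a shared order). Section 6 gives the purpose: "Conditions will be counterbalanced across participants to control for order effects". The same section fixes the number in the design, "Each participant (N = 4) will either be told that he/she is receiving Adderall or placebo", and shows one example order. It says of the contrast between what participants are told and what they are given: "This will allow for measurement of expectancy, which is a core measure for this study".

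The Study Summary gives the number of subjects as "10 (4 to complete the study, and 6 alternate participants". Section 9.3 provides for people who stop early: "If the participant does not complete the study, payments will be prorated to pay them for the visits they did complete". No section names a Latin square, lists the orders or says which order an alternate receives. The primary endpoint (section 3.2) is feasibility and acceptability, and section 10 anticipates no publication.

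**The concern.** The stated aim is control of order effects, but the only criterion spelled out is that participants differ in their order. That is weaker than balance. Four different orders can still place one told label early and the other late. The scanner tasks and the RBANS are repeated at each weekly session, so a practice effect is plausible and would then leak into the expectancy comparison. With four people, one badly placed order is a quarter of the data.

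Alternates sharpen the worry. If the ban on shared orders covers everyone enrolled, an alternate could not take over a dropout's order, and one replacement would break any Latin square. At stake is the comparison of cognitive performance by told label, which the protocol treats as central to its aim.

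**Working it through.** The protocol gives no figure to reproduce: it states no power, effect size or practice effect. The check is a count of orders.

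**Inputs.** Four conditions, four weeks and four completers (Study Summary, sections 3.1 and 6). Write A = told Adderall, given Adderall; B = told Adderall, given placebo; C = told placebo, given placebo; D = told placebo, given Adderall. The example order in section 6 is then ABCD.

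**Step 1: how weak is the bare rule?** There are 4! = 24 orders and C(24,4) = 10,626 sets of four different orders. Of these, 24 (24/10,626 = 0.23%) are Latin squares. Define the gap as the mean week of told-Adderall sessions minus the mean week of told-placebo sessions, averaged over participants. Over all sets the mean absolute gap is 0.48 weeks. The extreme is 2 weeks, reached by 2 of the 10,626 sets. One is ABCD, BACD, ABDC, BADC: told-Adderall falls in weeks 1 and 2 for everyone (mean 1.5) and told-placebo in weeks 3 and 4 (mean 3.5). Under an assumed linear practice gain of g per week, the unadjusted expectancy contrast would be off by 2g.

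**Step 2: can the text as written be followed with full balance?** Take ABCD, BCDA, CDAB, DABC. Each condition falls once in each week, no two participants share an order, and the first row is the protocol's own example. The participants' gaps are -2, 0, +2 and 0, which average to 0. Every sentence on order is satisfied.

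**Step 3: cost of the unfavourable reading for alternates.** Start from any of the 24 Latin squares, remove one of four participants and insert one of the 20 unused orders: 24 x 4 x 20 = 1,920 cases. None is still a Latin square.

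- Absolute gap of 0 / 0.25 / 0.5 / 0.75 / 1 week in 320 / 720 / 560 / 240 / 80 cases.
- Mean absolute gap = (720 x 0.25 + 560 x 0.5 + 240 x 0.75 + 80 x 1) / 1,920 = 720 / 1,920 = 0.375 weeks. The signed mean is 0.

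Code told-Adderall +1 and told-placebo -1. After adjustment for participant and week, the share of expectancy information kept is 1 - (sum over weeks of squared column totals) / 64. For example, replacing DABC by BACD in the square of step 2 gives column totals 2, 0, -2, 0. The share kept is 1 - 8/64 = 87.5%, and the gap is (-2 + 0 + 2 - 2)/4 = -0.5 weeks.

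- Over the 1,920 cases the share is 100% / 87.5% / 75% in 240 / 1,440 / 240 cases, with mean 87.5%.
- Standard error ratio: 1/sqrt(0.875) = 1.069 typically, 1/sqrt(0.75) = 1.155 at worst.

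If the alternate takes the replaced person's order, the gap is 0 and 100% is kept.

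**Step 4: would a tighter prescription gain anything?** Of the 24 Latin squares, 6 are Williams squares, which also balance first-order carryover. In 2 of these 6, every participant has a told-label gap of 0. In those two, however, each participant's gap between Adderall-given and placebo-given sessions is 1 or 2 weeks in either direction, and it cancels only across all four people. Balance within a person for expectancy is bought at the expense of the drug factor.

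**The case for a change.** The strongest case for a change is that the protocol fixes both a purpose and a criterion, and the criterion does not deliver the purpose. On that view this is a rule written badly, not a detail deferred. Section 3.1 speaks of all participants, which can be read to include alternates; on that reading the rule forbids the only replacement that keeps balance. The remedy would be a line of text, with no added participants or visits.

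Part of this stands. The protocol could be clearer, and step 1 shows that the no-shared-order clause by itself guarantees nothing about weeks. But the clause does not stand by itself. It qualifies a promise to counterbalance over the four weeks, and section 6 repeats the promise across participants. The 0.23% counts every set of different orders as admissible, which leaves the word counterbalanced without content. In any Latin square no two rows match, so the clause can be read as a plain consequence of the design.

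The argument on alternates rests on inference. The Study Summary names alternates without saying that they replace people already dosed. Screening in section 4.3 disqualifies some candidates before any order is used. Section 9.3 is a payment rule. Section 6 ties the design to four participants, and under that reading no conflict arises.

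**Conclusion.** The concern does not hold as a fault in the plan. What remains is missing detail: the set of orders is not named, and the alternate's order is not stated. A person preparing the schedule for four conditions, four weeks and four people would sensibly use a Latin square and let a replacement inherit the vacated order. Nothing in the protocol stands in the way, and the orders actually used may well have been balanced.

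The figures in step 3 are conditional on a Latin start, exactly one replacement of a dosed participant, a ban on reuse that extends to alternates, and equal weight on all 1,920 cases. Even then the effect is noise with mean zero: a typical standard error increase of about 7%, and about 15% at worst. The 2-week gap in step 1 needs a schedule that ignores the promise to counterbalance. The primary endpoint does not depend on order balance and no publication is anticipated. Naming the square in the protocol would be harmless, but it would correct no error.
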